6.4.1 Randomization Procedures

The NCC Data Manager, who will have no contact with participants or practices, will conduct randomization. Practices will be randomized to NRT or ET (approximately 25 practitioners per condition). Condition assignment will be stratified by practice level patient demographic data (highest percentage minority race/ethnicity vs. lowest) and practice payer mix (highest vs. lowest public insurance/free care). We will use block randomization with permuted block size of 2 and 4. Randomization will occur once the practice has completed all activities required for onboarding.

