To evaluate readiness for future implementation, we will conduct qualitative analyses of stakeholder interviews to gain insight into future implementation efforts. Using a structured debriefing form, post-interview notes will be written after each interview and reviewed by all Co-Is. Interviews will be professionally transcribed and deidentified. A qualitative expert will develop analytical codes using an iterative method in which interview notes are reviewed to: 1) consider whether the qualitative research agenda questions are appropriate and complete, 2) whether content saturation has been reached, and 3) develop an initial coding structure. Deductive codes will be drawn from the interview questions; inductive codes will capture concepts that emerge from the interviews. Once the coding scheme is developed, coders will independently code the transcripts and meet to resolve discrepancies. Final codes will be entered into NVivo qualitative data analysis software. A qualitative expert will conduct a framework matrix analysis⁶¹ to identify the most effective ways to organize the content and logistics of conducting the trial to help guide our trial protocol.^{61,62}

We will also report on descriptive statistics regarding the patient client satisfaction questionnaire, and the provider implementation measures.

Finally, we will conduct a cost effectiveness analysis (CEA). Our analyses will assess the incremental cost-per-quit and cost-per-quality adjusted life year (QALY) saved from a societal perspective and also a health system (e.g., accountable care organization) perspective in accordance with current practice recommendations.⁶³ The incremental cost-per-quit of NRTS vs. ET is estimated as: $(\text{Total costs at follow-up for NRTS participants} - \text{Total costs at follow-up for ET participants}) / (\text{Total successful quits at follow-up for NRTS participants} - \text{Total successful quits at follow-up for ET participants})$. The cost per QALY saved is estimated as $(\text{Total lifetime costs for NRTS participants} - \text{Total lifetime costs for ET participants}) / (\text{Total quality-adjusted life expectancy for NRTS participants} - \text{Total quality-adjusted life expectancy for ET participants})$.

The major direct costs for NRTS are described in the table below. Though some costs are incurred in both the NRTS and ET arms, we will measure them explicitly in the event that they do not entirely offset one another.

Cost data		

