Cost	Basis for valuation	NRTS and/or ET
RX for Change AAR dental training	Value of time	NRTS & ET
AAR provided to smokers	Value of time	NRTS & ET
ADA Brochures	Purchase/photocopy/printing cost	NRTS & ET
NRT	National average NRT purchase price ¹⁶²	NRTS
Counseling on NRT use	Value of time	NRTS
Additional smoking cessation medications and services*	National average purchase price ¹⁶²	NRTS & ET

*Applies only to societal-perspective analyses

Personnel time will be valued at the national average wage for the relevant job type. The value of time for clinical personnel who may bill for their services will be based on a prorated fraction of a billing unit specific to the clinician type. We will track all participants' use of smoking cessation services (counseling, medication), whether provided as part of the intervention or not, to determine the net impact of the intervention on treatment use. This will allow us to determine whether the intervention in any way crowds out cessation efforts that would have occurred absent the intervention. We will make the conservative assumption that the provision of an electric toothbrush to participants randomized to ET does not in itself affect cessation and so we will ignore the cost of the toothbrushes. For the cost-per-quit analyses, costs from Table 1 will be assessed for each participant during the full course of follow-up. For the cost per QALY analyses, differences in future health care costs will be estimated based on existing literature.^{64–67}

Cessation outcomes for the cost-per-quit analyses will be based on the study's primary outcomes. Quality-adjusted life expectancy will be estimated based on CDC life table data adjusted for smoking status and weighted by health utility (quality adjustment) data from prior studies.^{68–71}

We will use Monte Carlo simulation methods which aggregate uncertainty in parameter estimates (e.g., 95% confidence bounds) and develop confidence bounds on our cost-per-quit estimates. Following standard methods of economic evaluation in prior studies, we will also perform parameter-specific sensitivity analyses in which individual parameters are varied singly and in combination, through plausible ranges to assess the relative impact different elements of the program have on overall cost-effectiveness.^{72–75}

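### Both cost-effectiveness ratios are written as differences in arm totals, so unequal arm sizes moderately distort cost per quit and can badly distort cost per QALY

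*Protocol*

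**What the plan says.** Protocol section 12.3 writes out both ratios.

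- **Cost per quit.** The numerator is "Total costs at follow-up for NRTS participants" minus the same total for ET. The denominator is "Total successful quits at follow-up for NRTS participants" minus the ET count.
- **Cost per QALY.** The numerator is "Total lifetime costs for NRTS participants" minus the ET total. The denominator is "Total quality-adjusted life expectancy for NRTS participants" minus the ET total.

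The same section says that costs "will be assessed for each participant during the full course of follow-up", but not that they are then averaged. Section 6.4.1 allocates practices, "approximately 25 practitioners per condition", and states: "We will use block randomization with permuted block size of 2 and 4". Section 5 expects about 24 patients per practice and 1200 in all. Section 6.5.1 lets the investigator close sites for recruitment problems or once recruitment goals are met. Section 14.1 allows recruitment to be stepped up at selected offices.

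**The concern.** An incremental cost-effectiveness ratio compares what one more person treated costs and gains. A difference of arm totals measures that only when the arms have equal headcounts. Otherwise each surplus person in one arm adds a whole person's cost and outcome to the difference. The permuted blocks balance the number of practices within strata, not the number of patients, so an exact 600/600 split would be chance.

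For quits the added amount is small, because most participants contribute none. For QALYs every participant contributes a full remaining life expectancy, which is very large beside the gain from the intervention. At stake is Objective 5 (Hypothesis 5 in section 12.1), which is meant to inform implementation. The primary outcome is not affected.

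**Working it through.** **Check on design inputs.** The protocol states no cost-effectiveness figure, so only the arm sizes and quit rates can be checked against it. For 5.5% vs 10.5%, ICC 0.013 and 50 clusters of 24:

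- Effective n per arm = 600/(1 + 23×0.013) = 461.9.
- Unpooled SE = √[(0.055×0.945 + 0.105×0.895)/461.9] = 0.0178.
- Power = Φ(0.05/0.0178 − 1.96) = 80.3%, as in Table 11.1.

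**Assumed inputs (not in the protocol).** Cost per patient is $110 in NRTS and $30 in ET. Lifetime cost is $150,000 per person, plus $80 in NRTS. Baseline is 15 QALYs per person, with 1 QALY gained per quit, which gives means of 15.105 and 15.055.

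**Per-participant form.** Cost per quit = (110 − 30)/(0.105 − 0.055) = $1,600. Cost per QALY = 80/0.05 = $1,600. Neither depends on arm size.

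**Cost per quit from totals:** (n_N×110 − n_E×30)/(n_N×0.105 − n_E×0.055)

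| NRTS/ET | Cost difference | Quit difference | Ratio |
|---|---|---|---|
| 600/600 | $48,000 | 30.0 | $1,600 |
| 570/630 | $43,800 | 25.2 | $1,738 (+9%) |
| 630/570 | $52,200 | 34.8 | $1,500 (−6%) |

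**Cost per QALY from totals:** (n_N×150,080 − n_E×150,000)/(n_N×15.105 − n_E×15.055)

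| NRTS/ET | Cost difference | QALY difference | Ratio |
|---|---|---|---|
| 600/600 | $48,000 | +30.0 | $1,600 |
| 595/605 | −$1,452,400 | −120.8 | $12,023 |
| 605/595 | $1,548,400 | +180.8 | $8,564 |

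**Why so few people matter.** With arms of 600 + d and 600 − d, the QALY difference is 600×0.05 + d×(15.105 + 15.055) = 30 + 30.16d. Moving one person from NRTS to ET (599/601) cancels the whole gain: 30 − 30.16 = −0.16.

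**Range.** With quit rates of 4.7% and 10.2% (the preliminary ET rate and effect size in section 12.2), baselines of 10 to 30 QALYs and gains of 1 to 3 QALYs per quit, the QALY difference turns negative once NRTS is about 1 to 10 participants smaller than ET. In a simulation with 25 practices per arm, mean size 24 and an assumed coefficient of variation of practice size of 0.1 to 0.5, NRTS falls short by 7 or more with probability of about 35% to 47%.

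**The case against.** The strongest reply is that the formulas are shorthand for equal cohorts. Section 12.3 calls the ratios incremental, follows current practice recommendations, collects costs by participant, takes *differences* in future health care costs from the literature, and derives life expectancy from life tables by smoking status. That suggests a per-person model, and an analyst might never sum lifetimes over unequal arms. This is plausible, but no sentence divides by arm size. *Total costs* might mean all cost components, yet a total of successful quits can only be an arm count. The planned Monte Carlo and sensitivity analyses vary parameters and would not remove a headcount effect.

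A second reply is that cost per quit barely suffers. That stands: a shift of 6% to 9% is small beside sampling error. A 95% interval for the 5-point effect of about 1.5 to 8.5 points already spans about $940 to $5,300 per quit.

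A reader might infer that the cost-per-QALY ratio itself changes sign. In the 595/605 example it does not: both differences turn negative and the ratio stays positive but wrong. With lifetime costs totalled as written, the ratio is negative only in a narrow band. At 599/600, for example, the cost difference is −$102,080 and the QALY difference +14.9. It would also be negative if only programme costs were counted (at 595/605, $47,300/−120.8 = −$392), but the formula specifies lifetime costs.

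**Conclusion.** The two formulas are wrong as written; this is not detail left to a later plan. Applied literally, they give answers that depend on headcount. The distortion of cost per quit is moderate, about 6% to 9% at a 570/630 split either way under the stated assumptions. The incremental QALY total can change sign with an imbalance of a few participants, and cost per QALY is then badly wrong. A surplus in NRTS distorts it too.

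All unit costs, lifetime costs, QALY values and the spread of practice sizes are assumptions. The fragility of the QALY total held across every combination of baseline and gain tried. The documents do not show that the analysts will apply the formulas literally, so the point is that the text permits a wrong result, not that one is certain. It concerns a secondary economic objective and leaves the primary analysis, power and data collection untouched.

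**What to change.** In section 12.3, replace the arm totals in both formulas with means per enrolled participant:

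- Cost per quit = (mean cost in NRTS − mean cost in ET)/(quit proportion in NRTS − quit proportion in ET).
- Cost per QALY = (mean lifetime cost in NRTS − mean lifetime cost in ET)/(mean quality-adjusted life expectancy in NRTS − mean in ET).

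The cost is the rewording of two formulas. Participant-level costs and outcomes are already to be collected, so no new data are needed, and the results are identical if the arms turn out equal. Practice-level resampling, adjustment for clustering and net monetary benefit are separate method choices, and this correction does not need them.

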
Assess the cost effectiveness of the NRTS intervention.
	
To aid in future implementation, we will determine how much the intervention costs relative to how effective the intervention is at increasing abstinence from smoking.
	
We will assess cost per quit and cost per quality adjusted life year. Costs of the intervention will be determined by the value of time for practitioners to take the AAR training, provide AAR to patients, and counsel on NRT use, the costs for the ADA brochures, NRT (based on national average purchase price), and any additional smoking cessation services used by participants (based on national average purchase price). Quality adjusted life years will be estimated based on differences in future healthcare costs based on existing literature.
	
N/A

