7.4 Study Behavioral Intervention Description

Practices will be randomly assigned to study condition (NRTS or ET). Practices will be instructed not to disclose the intervention condition to the patient participant until after the baseline survey has been completed.

AAR (both conditions): Practitioners (NRTS and ET) will be encouraged to deliver AAR to all patients regardless of trial participation.

Patient participants will receive:

- monogrammed study bag
- study trinkets such as pens and post-it notes
- a brochure published by the ADA describing the effects of tobacco use on oral and general health
- contact information for their state tobacco quitline
- information about tobacco cessation medications
- study contact information
- the follow-up schedule
- condition specific information about NRT/ET
- consent form
- HIPAA form

NRT sampling (NRTS): Practices assigned to NRTS will dispense NRT samples in addition to AAR.

Patient participants will receive: a “starter pack” consisting of a 2-week supply of both nicotine patches (14 mg) and lozenges (4 mg; combination NRT [C-NRT]). Practitioners will spend 1-3 minutes on instruction prior to dispensing samples. Instructions for NRT use are provided on each medication package. We will also include FAQs and information dispelling misconceptions. Practitioners will neither explicitly advise nor discourage combined use or concomitant use with cigarettes. Patients will receive oral and written instructions including how to obtain more nicotine replacement therapy if interested (e.g., from their primary care provider, or purchased over the counter). Practitioners will instruct patients that the samples are an opportunity for smokers to learn about two NRT products that can be used individually or together (participant choice, including none at all). Some suggested uses could be:

- to get experience with the products and determine if they like them
- to reduce smoking or restrict where they smoke

- to make a practice quit attempt
- to get started on quitting

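### The health-system cost analysis excludes all follow-on cessation treatment, including any part the health system itself pays for

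*Protocol*

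**What the plan says.** Section 12.3 states that incremental cost per quit and cost per QALY will be estimated "from a societal perspective and also a health system (e.g., accountable care organization) perspective". Its cost table has a row headed "Additional smoking cessation medications and services", marked as arising in both arms and valued at a national average price. The footnote to that row reads "Applies only to societal-perspective analyses". No reason is given.

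The text after the table says that cessation counselling and medication will be tracked in all participants, "whether provided as part of the intervention or not, to determine the net impact of the intervention on treatment use", and that this will show "whether the intervention in any way crowds out cessation efforts that would have occurred absent the intervention". The table's costs are then to be summed per participant over all of follow-up for the cost-per-quit analysis.

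Section 4.2, in the row on cost effectiveness, counts among the costs "any additional smoking cessation services used by participants (based on national average purchase price". It names no perspective.

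Section 7.4 says that patients given the samples are told "how to obtain more nicotine replacement therapy if interested (e.g., from their primary care provider, or purchased over the counter". The Protocol Summary predicts higher NRT use under sampling, and Hypothesis 3a in Section 12.1 makes NRT use a mediator of the effect on abstinence.

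**The concern.** A health-system perspective should carry the costs that the health system bears and leave out those it does not. The footnote does not draw that line. It removes the whole row, regardless of payer.

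This matters because later treatment is part of how the intervention is expected to work. The samples are a two-week starter supply, and primary care is one of the two named sources of more. If some participants go on to treatment that an accountable care organization pays for, and quit as a result, those quits enter the denominator of the health-system ratio while their treatment cost stays out of the numerator. If sampling instead displaces treatment that the system would have paid for, the saving is lost from the numerator. The protocol treats displacement as possible and plans to look for it, but the footnote keeps the finding out of the health-system result.

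Objective 5 is meant to inform later implementation, so a health-system figure should reflect what a health system would pay.

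**Working it through.** **Step 1. Is there a figure to reproduce?** No. The protocol states no unit cost, no cost per quit, no uptake of additional treatment and no payer share. Only the sensitivity of the ratio to the omitted item can be calculated.

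**Step 2. Check the abstinence differences used as denominators.** Section 12.2 gives 50 practices of 24 patients (1200 in total, 600 per arm if equal), differences of 5.0 to 7.0 points, and 5.5 points in a similar study. Its power table can be reproduced. For an ICC of 0.013 and 5.5% against 10.5%:

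- Design effect = 1 + 23 × 0.013 = 1.299; effective n per arm = 600 / 1.299 = 461.9.
- Standard error = √[(0.055 × 0.945 + 0.105 × 0.895) / 461.9] = 0.01778.
- Power = Φ(0.05 / 0.01778 − 1.96) = 80.3%, the tabulated value.

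All 45 cells of the table agree to 0.1 point by this method, so the planning differences are a sound basis.

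**Step 3. Effect of the omitted row on cost per quit.** Section 12.3 defines incremental cost per quit as the difference in total costs divided by the difference in total quits. Let *c* be the mean additional medication and counselling cost per participant borne by the health system, NRTS minus ET, and *d* the abstinence difference. With equal arms of *n*:

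shift in cost per quit = (*n* × *c*) / (*n* × *d*) = *c* / *d*

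| *d* | Extra quits per 600 | Shift per $1 of *c* |
|---|---|---|
| 5.0 points | 600 × 0.050 = 30 | 1 / 0.050 = $20.0 |
| 5.5 points | 600 × 0.055 = 33 | 1 / 0.055 = $18.2 |
| 7.0 points | 600 × 0.070 = 42 | 1 / 0.070 = $14.3 |

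**Step 4. Range for *c*.** These values are assumptions; none is in the protocol.

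| Assumed *c* | *d* = 5.0 | *d* = 5.5 | *d* = 7.0 |
|---|---|---|---|
| −$10 (crowd-out) | −$200 | −$182 | −$143 |
| $0 | $0 | $0 | $0 |
| +$10 | +$200 | +$182 | +$143 |
| +$50 | +$1,000 | +$909 | +$714 |

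**Step 5. Cost per QALY.** The same cost is missing from that numerator. The protocol gives no QALY difference, so no size can be put on it.

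**Step 6. Would the planned sensitivity analyses reveal it?** Section 12.3 plans Monte Carlo simulation and variation of individual parameters. It does not say that these put the excluded row back into the health-system model.

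**The case against.** The strongest reply is that this is a scoping choice. A health-system view rightly excludes what the system does not pay for, and much follow-on treatment may fall there: patch, gum and lozenge are available over the counter, and the referral in both arms is to a state quitline. Only the primary care route points to a health system, and even there the protocol does not say who pays. Use of additional treatment is still measured in everyone and still costed in the societal analysis. This stands as far as it goes. It justifies excluding patient-paid and quitline-funded items. It does not justify excluding the part that the health system does pay for, which the footnote also removes.

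Three stronger readings are tempting, and the protocol does not support them:

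- A reader might infer that the footnote contradicts Section 4.2. That section is a summary without a stated perspective, and the cost it lists is counted in the societal analysis. It is unqualified, not contradictory.
- A reader might infer that the health-system cost per quit is misstated, or tilted towards NRTS. That requires a nonzero *c*, and a positive one for the tilt. The protocol fixes neither, and a net cost of zero changes nothing.
- A reader might infer that the follow-up surveys already separate health-system costs from others because they ask about use and purchase. Purchase does not identify the payer: a product not bought could come from a quitline, and a bought one could be partly covered. No listed item records who paid.

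**Conclusion.** The point holds in limited form. As written, the footnote drops all additional cessation medication and counselling from the health-system analysis, including any part that the health system bears, and so does not match the perspective that Section 12.3 names. The health-system cost per quit and cost per QALY can be misstated in either direction.

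What is established is leverage: a shift in cost per quit of 14.3 to 20.0 times the omitted net per-participant cost over the planned 5.0 to 7.0 point range. This assumes equal arms and abstinence differences as planned. The actual size and sign are unknown, because they depend on uptake, price and payer share, none of which the protocol gives. The primary outcome, the sample size, the effectiveness analyses and the societal analysis are unaffected. The change is worth making because it is cheap and the health-system figure is one of the two results planned under Objective 5.

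**What to change.** 1. Replace the blanket footnote with a rule by payer: additional medication and counselling borne by the health system enter both perspectives; over-the-counter products paid for by patients, and services funded by others such as the state quitline, stay in the societal analysis only.
2. Assign the payer by a stated assumption, using the health insurance item in the after-visit survey and the medication use and purchase and counselling items at 1, 3 and 6 months, or add one response option on who paid.
3. Report a sensitivity analysis in which the share of additional use paid by the health system runs from none (the present footnote) to all.
4. Align the cost-effectiveness row of Section 4.2 with Section 12.3 by stating which perspective each cost belongs to.

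The cost is revised wording, one more line in the health-system model, and reliance on a payer assumption that the sensitivity analysis makes visible. If the added response option is chosen, the follow-up surveys need a small change. If the sponsor prefers to keep the exclusion, the protocol should give the reason, and items 3 and 4 still apply.
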